**Table 16: Schedule of Assessments- Follow-up Period (Year 2 to Year 3)**

Assessment	Follow-up Period			
	Visit 25	Visit 26	Visit 27	Visit 28/ End of Study 
Day (± days)	Day 903 (±3 days)	Day 987 (±3 days)	Day 1071 (±3 days)	Day 1127 (±3 days)
ECOG	X	X	X	X
CT with contrast	X 	X 	X 	X 
ctDNA (central laboratory)	X 	X 	X 	X 
Serum CA-125/CEA/CA 19-9 (local laboratory)	X 	X 	X 	X 
Adverse events	X 	X 	X 	X 
Standard of care biopsy (local laboratory)	X 	X 	X 	X 

CA=carbohydrate antigen; CEA=carcinoembryonic antigen; CRC=colorectal cancer; CT=computed tomography; ctDNA=circulating tumor deoxyribonucleic acid; ECOG=Eastern Cooperative Oncology Group; IV=intravenous; MRI=magnetic resonance imaging; PDAC=pancreatic ductal adenocarcinoma;

1. A visit window of ±14 days is permitted for imaging assessments during the Follow-up Period. For subjects with IV contrast allergy/intolerance, MRI may be performed. Unscheduled CT imaging or MRI may be performed at any time, if the investigator determines that there are clinical signs of disease progression.
2. Serum biomarkers CA-125 [ovarian], CA19-9 [PDAC] or CEA [CRC]. Details for central laboratory sample collections are provided in the Central Laboratory Manual
3. ctDNA blood testing will occur at a central laboratory. Details for blood collection are provided in the Central Laboratory Manual
4. Long-term observation for post dose vaccination adverse events will be recorded if an adverse event began within 30 days of last dose of treatment and continues in the follow-up period. See [Section 6.7](#) for instructions regarding signs of toxicity.
5. If new lesions are observed on radiographic imaging, a standard of care biopsy may be performed per iRECIST criteria to confirm disease progression and when the investigator judges that tissue can be safely obtained. If there is sufficient tissue obtained from the biopsy, the pathology lab should perform in situ gene expression and/or IHC for evaluation of tumor infiltrating T cells and the tumor microenvironment.

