#### **13.3.4. Safety Analysis**

Summary statistics (counts, percentage, mean, standard deviation, etc.) will be provided for the safety endpoints as appropriate.

Treatment-emergent adverse events (TEAEs) will be listed and tabulated by system organ class, preferred term, maximum CTCAE grade, relationship to trial treatment, outcome, and action taken with trial treatment. TEAEs will be tabulated by treatment regimen and overall and reviewed for potential significance and clinical importance. Adverse events qualifying as serious will be separately listed, along with any dose interruptions and reductions.

Significant PE findings and vital signs will be listed and summarized by treatment regimen. Clinical laboratory results will be presented in a listing including change from baseline and selected parameters will be summarized in shift tables. ECG derived data will be explored graphically and by summary statistics.

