## 9.0 STUDY ENDPOINTS

### 9.1 Endpoints

#### 9.1.1 Phase 1 Primary Endpoints

- To define the MTD of ELI-002 (in the event there is an MTD) and the recommended Phase 2 dose (RP2D)
- To evaluate safety as assessed by the incidence of adverse events (AEs) and clinically significant changes in laboratory tests and vital signs

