### **13.7.2 Clinical laboratory evaluations**

Laboratory assessments comprise safety laboratory tests (hematology, blood chemistry and coagulation), serum cytokines, pregnancy and viral laboratory screening tests. For the purposes of summarization in both tables and listings, all laboratory values will be presented in SI units. If a lab value is reported using a nonnumeric qualifier e.g., less than (<) a certain value, or greater than (>) a certain value, the given numeric value will be used in the summary statistics, ignoring the nonnumeric qualifier.

Laboratory test results and change from baseline of serum cytokine, worst on treatment hematology and chemistry results will be summarized using descriptive statistics by cohort/dose level, scheduled, and unscheduled visits.

For all clinical laboratory result listed in the protocol and captured by the CRF, by-subject, by-visit listings will be provided and abnormal flags (low or high) will be provided.

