### **13.7.3 Vital signs**

All vital sign measurements will also be presented in a by-subject listing.

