## 14.0 CHANGES TO PLANNED ANALYSIS FROM STUDY PROTOCOL

The protocol has indicated that statistical testing and confidence intervals would be computed for the efficacy analyses; however, since the sample sizes are small and efficacy data from this trial are exploratory and not powered to elicit statistically significant treatment effects, no formal statistical testing will be computed except for RFS and OS endpoints. ctDNA and Immunogenicity analyses are beyond the scope of this document and are specified in a separate addendum which is attached here as an appendix.

Additional exposure outcomes namely Dose Intensity (DI) and Relative Dose Intensity (RDI) not mentioned in the protocol will be summarized for better clarity on the treatment exposure.

The protocol has requested that summary statistics be presented for patient reported outcomes, however, due to the early termination of the long term follow up of the study, only by-subject listing will also be provided for these endpoints.

The protocol has requested the use of the Disease Response Evaluable Set population, however, as no outputs in the SAP/shells are based on this set, it was dropped from the SAP.

**Final Analysis  
Statistical Analysis Plan (SAP)**

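### The SAP omits the protocol's vital-sign summary and laboratory shift tables without declaring it, and its reason for dropping PRO summaries cannot cover the visits before follow-up

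*SAP*

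**What the plan says.** The second primary endpoint (SAP 9.1.1, matching the protocol synopsis) covers the incidence of adverse events and "clinically significant changes in laboratory tests and vital signs".

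On reporting, Protocol 13.3.4 states: "Significant PE findings and vital signs will be listed and summarized by treatment regimen". For laboratory results it plans a listing with change from baseline, and adds that "selected parameters will be summarized in shift tables".

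The SAP's vital-signs section (13.7.3) is one sentence: "All vital sign measurements will also be presented in a by-subject listing". For laboratory data, SAP 13.7.2 plans summaries of serum cytokines and says that "worst on treatment hematology and chemistry results will be summarized using descriptive statistics by cohort/dose level, scheduled, and unscheduled visits", with flagged listings. The only shift table in the SAP is for ECOG status (13.7.6).

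SAP 14.0 lists the departures from the protocol: statistical testing and confidence intervals, added dose-intensity measures, PRO summaries, and the dropped Disease Response Evaluable Set. On PROs it says that "due to the early termination of the long term follow up of the study, only by-subject listing will also be provided for these endpoints". PRO change from baseline remains an exploratory endpoint in SAP 9.1.3. SAP 12.4 gives full scoring rules, and SAP 13.8.3 still has the scale scores calculated.

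**The concern.** Two things look wrong, and they differ in kind.

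The first is an undeclared change to how part of a primary endpoint is reported. A shift table shows how many subjects at each dose moved from normal to abnormal. Descriptive statistics of worst values do not. Worst is also undefined for analytes that can be abnormal in either direction, such as sodium, potassium and glucose (all in the panel in Protocol 12.1.6.3). A worst on-treatment value is normally one per subject, so it is unclear how it would be summarised by visit. For vital signs, the SAP text specifies no summary by dose at all.

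The second is a declared change whose reason does not fit most of the data it removes. Most post-baseline PRO visits come before follow-up begins. At stake is whether a reader of the study report can see the safety data in the form the protocol planned, and whether PRO data collected during treatment are left unsummarised for a reason that does not concern them.

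**Working it through.** The plan gives no figure to reproduce here. The check is a comparison of texts, a count of visits, and an illustration of precision.

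**1. Safety reporting, side by side**

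| Data | Protocol 13.3.4 | SAP 13.7.2-13.7.3 | Declared in SAP 14.0? |
|---|---|---|---|
| Vital signs | Listed and summarised by regimen | Listing only | No |
| Laboratory, selected parameters | Shift tables | No shift table; descriptive statistics of worst hematology and chemistry | No |
| Coagulation | Not singled out | Named as a safety test; no summary named | No |

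**2. Do the adverse event tables fill the gap?**
Protocol 12.1.6 has clinically significant laboratory values recorded as adverse events. SAP 13.7.1 tabulates treatment-emergent events by cohort, term and maximum grade. Clinically significant laboratory changes therefore do get a count per dose. The vital-signs section (Protocol 12.1.2) has no matching rule. The general definition in Protocol 12.2.1.1 is broad enough to admit a significant vital-sign change as an adverse event, but nothing requires it to be recorded as one.

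**3. PRO visits (Protocol Tables 11-16)**

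| Period | Visits | PRO visits |
|---|---|---|
| Screening and baseline | 2-3 | 2 |
| After first dose, to end of treatment | 4-15 | 12 |
| Follow-up, Table 15 | 16-24 | 9 |
| Follow-up, Table 16 | 25-28 | 0 of 4 |

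Total: 2 + 12 + 9 = 23, of which 12 + 9 = 21 are post-baseline. SAP 8.3 places the Follow-up Period at Visits 16 to 28.
- If only Visits 25-28 were cut, no PRO visit is lost.
- If all follow-up was cut, 9 of 21 post-baseline visits (43%) are lost and 12 of 21 (57%) remain.

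Visit 15 is Day 217 and first dose is Day 57, so the unaffected visits run to 217 - 57 = 160 days after first dose.

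The documents give no termination date. As an illustration, assume the last subject's first dose fell between 1 April and 31 August 2023 and follow-up stopped in August 2024, the month of SAP version 3.0. The study day reached is 57 plus the days elapsed.
- Latest cut: 1 April 2023 to 31 August 2024 is 518 days, so Day 575. Visits 22-24 are missed.
- Earliest cut: 31 August 2023 to 1 August 2024 is 336 days, so Day 393. Visits 19-24 are missed.

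No PRO visit up to Visit 15 is lost in either case.

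**4. Precision of a PRO summary**
The 95% half-width for a mean change is t × SD / √n. The SD is not in the documents. I assume 20 points and show 15 and 25 as a range. The n values are 18 (planned total), 30 (five cohorts of 6, SAP 8.1), and 6 and 3 (cohort sizes). All subjects are assumed to answer.

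| n | t | t/√n | SD 15 | SD 20 | SD 25 |
|---|---|---|---|---|---|
| 30, pooled | 2.045 | 0.373 | 5.6 | 7.5 | 9.3 |
| 18, pooled | 2.110 | 0.497 | 7.5 | 9.9 | 12.4 |
| 6, one cohort | 2.571 | 1.050 | 15.7 | 21.0 | 26.2 |
| 3, one cohort | 4.303 | 2.484 | 37.3 | 49.7 | 62.1 |

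Pooled summaries carry some information. Cohort summaries are descriptive only.

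**The case against.** The strongest reply is that little is lost. Laboratory data keep descriptive summaries and flagged listings, and the protocol promised shift tables only for unnamed selected parameters. Clinically significant laboratory values are counted by cohort as adverse events. The PRO change is declared, PROs are exploratory, the data are still listed, and Protocol 13.3 has no PRO analysis section. With 3 to 6 subjects per cohort, listings are defensible. SAP 6.0 also puts the table templates in a separate document, so a vital-sign table may exist there.

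Much of this stands. It limits the size of the point and rules out three stronger readings that a reader might infer:

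- *Laboratory safety yields no rate by dose.* The documents do not support this, because the adverse event route supplies one for clinically significant values.
- *The choice of recommended Phase 2 dose depends on these tables.* SAP 8.1 has that dose communicated after the last Safety Monitoring Committee cohort review. Nothing ties it to this final analysis.
- *Early termination touched no PRO data, because none is scheduled in Year 2 to Year 3.* This would need the terminated phase to mean Visits 25-28 only. The SAP never says so, and nine PRO visits fall in Visits 16-24.

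Two things do not stand. Unseen templates do not replace a specification, and the word *also* in SAP 13.7.3 refers to no summary that the SAP describes. And declaring the PRO change does not make its reason apply to visits that come before follow-up.

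**Conclusion.** The point holds in a limited form. The SAP departs from Protocol 13.3.4 on vital signs and on laboratory shift tables without saying so in SAP 14.0, although both data types are part of a primary endpoint. The vital-sign gap is the clearer one, since no summary is specified and no rule sends significant changes to the adverse event tables. The laboratory gap is one of format and definition: no shift, no direction for worst, and no named summary for coagulation.

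For PROs, the stated reason cannot justify dropping summaries at Visits 4-15, which are 12 of 21 post-baseline visits. Between none and all of the other nine may be affected, depending on an undefined phase and an unstated date. The conclusion about Visits 4-15 needs no assumption about that date, because those visits come before the Follow-up Period by design. The half-widths of 7.5 to 10 points apply only to pooled subjects at an assumed SD of 20. At the same SD, single cohorts of 6 or 3 give about 21 or 50 points, so cohort PRO tables would not support inference.

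**What to change.** - **SAP 13.7.2:** restore baseline-to-worst shift tables for hematology, chemistry and coagulation, by CTCAE grade or by low/normal/high, with low and high shown separately.
- **SAP 13.7.3:** add summaries of observed values and change from baseline by visit, by cohort and overall. Counts of clinically significant vital-sign changes would need thresholds that the documents do not give, so they are not asked for here.
- **SAP 13.8.3 and 14.0:** summarise observed and change-from-baseline QLQ-C30 scale scores by visit through Visit 15, overall and by cohort, labelled as descriptive. State which visits the terminated long-term follow-up covers and its cut date.
- **SAP 14.0:** declare and justify any remaining departure from Protocol 13.3.4. This includes physical examination findings, which are also listed only, and ECG, where a reason is given in SAP 13.7.5 but not in 14.0.

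No new data are needed. The PRO scoring rules are already in SAP 12.4, and low/high laboratory flags are already planned for the listings. The cost is a few extra tables, with low precision in each cohort.

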## LIST OF ABBREVIATIONS AND DEFINITION OF TERMS

---

Abbreviation	Definition
% CV	Coefficient of Variation
AMP-CpG	Amphiphile – Cytosine phosphoguanine
CD4	Clusters of Differentiation 4
CD8	Clusters of Differentiation 8
ctDNA	Circulating Tumor Deoxyribonucleic Acid
CSV	Comma-Separated Values
DFR	Distribution Fee Resampling
FS	Fluorospot
ICS	Intracellular Cytokine Staining
IFN	Interferon
IFNg	Interferon Gamma
IVS	In vitro simulated
LOQ	Limit of Quantification
mL	milliliter
MTM/mL	Mean Tumor Molecules per mL
NS	Non-stimulated
TNF $\alpha$	Tumor Necrosis Factor alpha
VAF	Variant Allele Frequency

## 1. BACKGROUND

*Please refer to Protocol ELI-002-001 and Statistical Analysis Plan.*

### 1.1. Objective

The objectives of this analysis are:

- o To assess reduction in ctDNA
- o To assess immune response at each timepoint based on
  - o Ex vivo Intracellular cytokine staining (ICS)
  - o Ex vivo Fluorospot
  - o In vitro stimulated (IVS) Fluorospot
  - o IVS ICS
  - o Ex vivo Dextramer
  - o IVS Dextramer.

The objectives will be assessed at up to five dose levels (0.1, 0.5., 2.5, 5 and 10 mg AMP-CpG).

### 1.2. Study Design, Sample Size, Dosing and Sample Collection

*Please refer to Protocol ELI-002-001 and Statistical Analysis Plan.*

A table of sample collection is below:

**Table 1-1 Collection of Immunogenicity and ctDNA Samples**

Visit	Week	Immunogenicity	ctDNA
2	Baseline	X (Baseline)	X
3 (First dose)	0		X (Baseline)
4	1		
5	2	X	
6	3		X
7	5	X	
9	9	X	
11	17	X	X
12	20		X
14	22	X	
16	25	X	X
17	29		X
18	37		X
19	49		X
20	61		X
21	73		X
22	85		X
23	97		X
24	105		X

Visits labeled "unscheduled", or the equivalent may be collected,

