## 10.5. Follow-up Period

A Follow-up Period will provide safety and efficacy data ([Table 15](#) and [Table 16](#)).

At every visit during the Follow-up Period, **Visit 16 (Day 231), Visit 17 (Day 259), Visit 18 (Day 315), Visit 19 (Day 399), Visit 20 (Day 483), Visit 21 (Day 567), Visit 22 (Day 651), Visit 23 (Day 735), Visit 24 (Day 819), Visit 25 (Day 903), Visit 26 (Day 987), Visit 27 (Day 1071) and Visit 28/End of Study (Day 1127)**, the following visit procedures will include:

- Confirm ECOG Scale of Performance Status.
- Collect a blood sample for ctDNA test (central laboratory).
- Record any AEs that occur within 30 days of last dose and follow any such AEs until they resolve or return to baseline level.

In addition, the following assessments will be conducted at these Follow-up visits:

At **Visit 16 (Day 231)**, the following visit procedures will include

- Collect a blood sample for clinical laboratory assessments, including the cytokine panel (local laboratory; see [Section 11.1](#) and [Section 12.1.6](#)).
- Collect a whole blood sample for immunogenicity testing (central laboratory).

At **Visit 16 (Day 231), Visit 17 (Day 259), Visit 18 (Day 315), Visit 19 (Day 399), Visit 20 (Day 483), Visit 21 (Day 567), Visit 22 (Day 651), Visit 23 (Day 735), and Visit 24 (Day 819)** the following visit procedures will include

- Administer the EORTC QLQ-C30 and the tumor type-specific PRO (see [Section 11.3](#)).
- Record vital signs (blood pressure, pulse rate, body temperature, and respiratory rate). Measurements will be obtained after 3 minutes in the sitting position. No other measurements or procedures were performed during this 3-minute period.
- Record weight.

At **Visit 17 (Day 259), Visit 19 (Day 399), Visit 20 (Day 483), Visit 21 (Day 567), Visit 22 (Day 651), Visit 23 (Day 735), Visit 24 (Day 819), Visit 25 (Day 903), Visit 26 (Day 987), Visit 27 (Day 1071), and Visit 28/End of Study (Day 1127)**, the following visit procedures will include:

- Perform a CT ( $\pm 14$  days) with contrast. For subjects with IV contrast allergy/intolerance, MRI may be performed. The same modality as the screening imaging assessment should be used throughout the trial.
- Collect a serum sample for CA-125/CA 19-9/CEA for appropriate tumor type (local laboratory).

At **Visit 20 (Day 483)**, the following visit procedures will include:

- Perform a physical examination, which will be based on institution standard of care (see [Section 12.1.3](#)).

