At **Visit 22 (Day 651)**, the following visit procedures will include:

- Collect a whole blood sample for immunogenicity testing (central laboratory).

The **Visit 28/End of Study** visit will be scheduled for subjects who complete the study or for any subject that discontinues from the study early.

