
Clearance
	
Define as the percent change from baseline of the on-study ctDNA, or CA19-9, or CEA that achieved -100%.
 
Notes:
 
 
a. Clearance start will be the date of first clearance.
 
b. Once clearance start date is identified for a biomarker, the same biomarker will be used to determine the clearance end date.
 
c. Results will not be considered if a subject has already started taking subsequent anti-cancer therapy.
 
d. If there is a tie for best response across biomarkers, select ctDNA first.                             
 
▪ For PDAC subjects, select CA19-9 second, CEA third.
 
• For CRC subjects, select CEA second, CA19-9 third.
 
 
 

Reduction
	
Defined as the percent change from baseline of the on-study ctDNA, or CA19-9, or CEA that achieved any decrease (i.e., a negative percent change from baseline).
 
Notes:
 
 
a. Reduction start will be the date of first reduction.
 
b. Once reduction start date is identified for a biomarker, the same biomarker will be used to determine the reduction end date.
 
c. Results will not be considered if a subject has already started taking subsequent anti-cancer therapy.
 
d. If there is a tie for best response across biomarkers, select ctDNA first.                             
 
• For PDAC subjects, select CA19-9 second, CEA third.
 
• For CRC subjects, select CEA second, CA19-9 third.
 
 
 

Duration of Biomarker Clearance/Reduction
	

Clearance Duration
	
This is confirmed after clearance start by an increase above -100% change from baseline followed by a second increase above -100% at least 1 week afterwards.
 
Notes:
 
 
a. The end date will be the date of the first subsequent increase.
 
b. If the increase cannot be confirmed by a second increase, then the potential end date of biomarker clearance will proceed to the next increase and so on.
 
c. Subjects with confirmed clearance duration will not be censored.
 

Reduction Duration
	
This is confirmed after reduction start by an increase above the initial reduction followed by a second increase above the initial reduction at least 1 week afterwards.

**Final Analysis  

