## 13.0 STATISTICAL METHODS

### 13.1 General Statistical Conventions

All statistical procedures will be completed using SAS version 9.4 or higher.

No formal tests of hypotheses are planned for analyses described in this document. Nominal p-values may be computed for secondary or exploratory efficacy analyses as a descriptive measure of strength of results rather than for formal tests of hypotheses.

**Unless otherwise stated, all summary tables and summary figures will be presented by cohort/dose level and scheduled visits (if applicable).**

All specified visit assessments described in protocol section 6.1.4 will be included in the analyses. If more than one visit assessments (not labeled as unscheduled) are available, only consider the chronologically most recent assessment for the analyses.

All subject data, including unscheduled visit results and derived data, will be presented in listings sorted by cohort/dose level, scheduled visit, and subject number in chronological order (if applicable).

Efficacy data will be listed by patient. Continuous variables will be summarized using mean, standard deviation, median, minimum value, maximum value; categorical variables will be summarized using frequency counts and percentages; and time to event data will be summarized using the Kaplan-

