## 2.2. ctDNA

ctDNA response is defined as the absence or reduction of circulating tumor DNA post-baseline. Analysis of ctDNA will be based on results from two laboratories and will be performed separately.

Duration of response is defined as the time in weeks from reduction until the date of increase or presence of ctDNA.

Any patient with detectable ctDNA at baseline whose post-baseline result is less than the baseline value or undetectable will be considered a responder. The number and percentage of responders will be reported.

Doubling will be calculated as the number of weeks between visits where ctDNA first doubles.

Doubling time and response will be based on the tumor molecules per mL (MTM/mL) and Variant Allele Frequency (VAF).

ctDNA levels over time will be summarized using descriptive statistics.

Data listings will present ctDNA values (VAF and MTM/mL) over time, ctDNA response, and duration of response, and time until doubling of ctDNA.

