DATE: HH:MM/DDMMYY

Protocol ELI-002-001                      Elicio Therapeutics, Inc.                      Confidential                      Page 1 of x

Table 7  
 Summary and Change from Baseline for ctDNA (ctDNA  
 Population)

Baseline	Baseline (1)	Cohort 1 (N=xx)	Cohort 1 (N=xx)	Cohort 1 (N=xx)
		N (2)	xx	--
		Mean (SD)	xx.x (xx.xx)	
		Median Min,	xx.xx xx.x	
		Max	xx.x	
		N Undetectable (3)	xx.x, xx.x xx	
		<repeat for remaining visits with at least 3 subjects		
Visit 6		N (2)	xx	xx
		Mean (SD)	xx.x (xx.xx)	xx.x (xx.xx)
		Fold Change Mean	xx.xx	xx.xx
		Fold Shange SD- SD	xx.x	xx.x
		Median	xx.x	xx.x
		Min, Max	xx.x, xx.x	xx.x, xx.x
		N Undetectable (3)	xx	xx
Doubling Time	N(4)	Mean (SD)		
		Median		
		Min, Max		
Clearance Duration (weeks)	N(5)	Mean (SD)		
		Median		
		Min, Max		
Response Rate	n%			

[1] Baseline is based on Visit 3 result or Visit 2 if Visit 3 is missing  
 [2] N reflects the number of patients with detectable concentrations of ctDNA .

[3] Number of subjects with results below the limit of detection. [4] N reflects the subjects whose ctDNA doubled.

[5] N reflects subjects whose ctDNA was undetectable or decreased post-baseline.

[REPEAT univariate statistics For VAF + MTM/ML by Assay]

Notes for programming: Timepoints –

- Visits 2, 3 (pre-vaccination)
- Visits 6, 11, 12, 16, 17, 18, 19, 20, 21, 22, 23, 24 (post-vaccination)

Elicio Therapeutics, Inc.  
Protocol ELI-002-001

Confidential

[figure not shown]
Page 1 of x

Figure 1

Ex vivo Fluorospot

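### The SAP addendum's visit lists omit the Visit 22 immunogenicity sample and the Visit 25 to 28 ctDNA samples that the protocol schedules

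*SAP*

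**What the plan says.** **Protocol.** In Section 10.5 the instruction for Visit 22 (Day 651) is "Collect a whole blood sample for immunogenicity testing (central laboratory", and Table 15 marks the same draw. For every follow-up visit, in a list that ends with "Visit 27 (Day 1071) and Visit 28/End of Study (Day 1127", Section 10.5 says "Collect a blood sample for ctDNA test (central laboratory". Table 16 marks ctDNA at Visits 25, 26, 27 and 28.

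**SAP addendum.** Table 1-1 ("Collection of Immunogenicity and ctDNA Samples") marks immunogenicity at Visits 2, 5, 7, 9, 11, 14 and 16. It marks ctDNA at Visits 2, 3, 6, 11, 12 and 16 to 24. Its Visit 22 row is marked for ctDNA only, and it has no rows for Visits 25 to 28. The programming note under addendum Table 7, the ctDNA summary, gives the post-baseline time points as "Visits 6, 11, 12, 16, 17, 18, 19, 20, 21, 22, 23, 24 (post-vaccination".

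**Main SAP.** In the schedule in SAP Table 6 the PBMC row is marked at Visit 16 only, while SAP Table 7 keeps ctDNA at Visits 25 to 28. Section 13.1 states: "All specified visit assessments described in protocol section 6.1.4 will be included in the analyses". Sections 9.1.3, 13.8.2 and 14.0 place the immunogenicity analyses outside the main SAP and in the addendum.

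**The concern.** The main SAP hands immunogenicity to the addendum, so the addendum's visit list is the one that a programmer is likely to follow. That list and SAP Table 6 both lack the protocol's last T-cell sample.

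The sample has a specific use. The protocol justifies the booster doses, and later the extension protocol, by the need to sustain antigen-specific T cells. Protocol Section 13.3.2 promises summaries of the immune response for every time point tested. If the latest tabulated sample is Visit 16, the tables describe the response shortly after the last booster and say nothing about persistence.

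For ctDNA, the addendum's by-visit table would stop before the last four scheduled assessments. Addendum Table 7 also reports doubling time and clearance duration. A programmer who applies its time-point note to those rows would derive them from fewer data than the main SAP uses.

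**Working it through.** **Reproducing Table 1-1.** The inputs are the protocol study days (Tables 12 to 16), with the first dose on Day 57. Week = (study day − 57)/7, rounded.

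| Visit | Day | Calculation | Week | Table 1-1 |
|---|---|---|---|---|
| 16 | 231 | 174/7 = 24.9 | 25 | 25 |
| 22 | 651 | 594/7 = 84.9 | 85 | 85 (ctDNA only) |
| 23 | 735 | 678/7 = 96.9 | 97 | 97 |
| 24 | 819 | 762/7 = 108.9 | 109 | **105** |
| 25 | 903 | 846/7 = 120.9 | 121 | no row |
| 26 | 987 | 930/7 = 132.9 | 133 | no row |
| 27 | 1071 | 1014/7 = 144.9 | 145 | no row |
| 28 | 1127 | 1070/7 = 152.9 | 153 | no row |

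Every other week printed for Visits 3 to 21 also reproduces. Visit 24 is the only error.

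**Comparing the visit sets.**

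- Immunogenicity: the protocol has Visits 2, 5, 7, 9, 11, 14, 16 and 22, which is 8 visits, 7 of them post-baseline. Table 1-1 has 7 and 6. The missing visit is Visit 22, 1 of 7 post-baseline.
- ctDNA: the protocol has Visits 2, 3, 6, 11, 12 and 16 to 28, which is 18 visits, 16 of them post-baseline. Table 1-1 has 14 and 12. The missing visits are 25 to 28, 4 of 16 post-baseline.

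**What the missing visits cover.** The last scheduled dose is on Day 217.

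- Visit 16 falls (231 − 217)/7 = 2 weeks after it.
- Visit 22 falls (651 − 217)/7 = 62 weeks after it, with no other immunogenicity sample after Visit 16.
- The ctDNA visits without a row run to the end of scheduled follow-up, (1127 − 819)/7 = 44 weeks beyond Visit 24.

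**Does the ctDNA gap reach the duration endpoint?** Main SAP Table 8 ends clearance at "an increase above -100% change from baseline followed by a second increase above -100% at least 1 week afterwards", and reduction by a similar rule. Neither rule has a visit limit. Addendum Section 2.2 says "Duration of response is defined as the time in weeks from reduction until the date of increase or presence of ctDNA", also without one, and the footnote to its ctDNA listing works from dates. The Visit 24 limit therefore appears only in Table 1-1 and in the Table 7 time-point note.

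**Is the omission declared?** SAP Section 14.0 lists departures from the protocol and attributes one of them, the loss of summary statistics for patient-reported outcomes, to the early end of long-term follow-up. It mentions neither Visit 22 immunogenicity nor ctDNA Visits 25 to 28.

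**The case against.** The best defence is that a missing mark in a collection table does not exclude a sample from analysis. Addendum Section 1.2 refers the reader to the protocol and SAP before showing Table 1-1. The addendum's objective is the immune response at each time point, its Fluorospot and ICS shells use a generic visit label, and its Immunogenicity Population takes anyone who contributes any immunogenicity data. A Visit 22 result would fit all of these rules. This stands against a flat statement that the sample will not be analysed. It does not remove the problem, because the addendum's only visit list for these samples lacks Visit 22 and SAP Table 6 repeats the gap. The general rule in SAP Section 13.1 is weaker support here, since the main SAP places immunogenicity outside its own scope.

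A reader might infer that stopping ctDNA at Visit 24 turns a later reappearance into an ongoing response. The documents do not support that. The duration definitions have no such limit, Section 13.1 brings in all visits of protocol Section 6.1.4, and SAP Table 7 retains ctDNA at Visits 25 to 28.

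A third objection is that the late samples may be few. Long-term follow-up ended early, cohorts have 3 to 6 subjects, and the addendum Table 7 shell repeats only for visits with at least 3 subjects. Visits 25 to 28 might not be tabulated even if listed. This stands, and it limits the practical effect.

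Little should be made of dates. The addendum is dated February 2023 and protocol Version 8.0 August 2023, but the SAP was revised after that, and the documents do not show whether Visit 22 was in the protocol when the addendum was written.

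**Conclusion.** This is a minor but real mismatch that is cheap to correct. Addendum Table 1-1 and SAP Table 6 omit the Visit 22 PBMC sample. Table 1-1 and the addendum Table 7 note end ctDNA at Visit 24, against the protocol and against SAP Table 7. If the outputs are programmed to those lists, the addendum loses its only T-cell time point after Visit 16 (62 weeks after the last scheduled dose, against 2), and its ctDNA table loses 4 of 16 post-baseline visits.

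The conclusion depends on the lists being followed as written, because the surrounding text would allow the samples in. It does not extend to the main SAP's clearance and reduction durations, where late reappearance still counts. The Week 105 label is a slip, and no estimate is shown to depend on it.

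The number of affected subjects cannot be stated. The synopsis plans first enrolment in 4Q2021. If the first dose also fell in that quarter (an assumption), 594 days later is mid-May to mid-August 2023, so some Visit 22 samples are plausible. The documents do not confirm that any exist.

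**What to change.** For all samples obtained before follow-up closed:

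- Add Visit 22 to the immunogenicity column of Table 1-1, to the PBMC row of SAP Table 6, and to the addendum's immunogenicity tables, figures and listings.
- Add ctDNA Visits 25 to 28 to Table 1-1 and to the addendum Table 7 note, so that the addendum's durations and doubling times draw on the same data as the main SAP. The two duration rules will still differ, because only the main SAP requires a confirming second increase.
- If any of these visits are deliberately dropped because follow-up ended early, say so in SAP Section 14.0, with the reason and the number of samples affected.
- Correct Visit 24 to Week 109.

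The cost is an edit to three visit lists and the matching program lists. It needs no new visits or change of method. If late samples exist but have not been assayed, that laboratory work is an additional cost, which the documents do not allow to be estimated.
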